9.2 Study Procedures

Please see study schema (Appendix C) for study flow.

Pre-Transfusion

- Once identified by Epic scheduling report, provider suggestion, or study-specific Epic Workbench report, eligible patients will be approached for consent discussion at an appointment with their provider.
 - Patients with Hb approaching 8.5 g/dL will be approached at an appointment prior to an upcoming transfusion.
 - Patients that are transfusion-dependent will be approached at an upcoming appointment with their provider or during a transfusion appointment.
- During this initial encounter, consenting participants will be given a study packet containing a paper copy of the QUALMS. Study participants will be instructed to fill out the survey on the day before their upcoming pRBC transfusion.

**PROTOCOL TITLE: A New Paradigm of Transfusion Decision Support for Patients with MDS:
Using Peri-Transfusion Quality of Life Assessments (PTQAs)**

3. Study participants will indicate whether they would like to receive PTQA reports in person, via mail, or via email.
4. Site RAs will call study participants using script (see Appendix D) on the day prior to an upcoming transfusion to remind them to complete the QUALMS and bring it with them to their transfusion.
5. Note: Index transfusion is defined as any upcoming transfusion appointment for which the participant has completed both the pre- and post-transfusion QUALMS questionnaires.
 - If a participant does not complete the pre-transfusion questionnaire for any reason (i.e., participant forgot to complete at home or forgot to bring in), then the RA may ask the participant to complete the questionnaire at home prior to a subsequent transfusion appointment. This subsequent transfusion will become the index transfusion.
 - If a participant does not complete the pre-transfusion QUALMS at home prior to the appointment and there are extenuating circumstances (i.e., participant does not regularly receive transfusions at the site), then the RA may ask the participant to complete the questionnaire in clinic before his/her planned index transfusion.

Post-Transfusion

6. On the day of transfusion, the site RA will collect the completed pre-transfusion QUALMS survey. Study participants will then receive a second paper copy of the QUALMS, along with a stamped envelope addressed to the appropriate site.

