7. Participants will be instructed to complete this survey exactly one week after transfusion and return it using the pre-addressed, pre-stamped envelope.
8. Site RAs will call participants using script (see Appendix D) to remind them to complete the QUALMS survey exactly one week after transfusion.
 - The window may increase up to one extra week to accommodate for circumstances where the patient is unable to complete the post-transfusion QUALMS (i.e., participant does not feel well or participant forgot).

PTQA Report

9. Once received, the second assessment will be scored and compared with the first, and both the patient and provider will be sent a report with the results. The QUALMS validation study suggested that a clinically meaningful difference on the instrument is between 5 and 10 points;¹² For this study:
 - A post-transfusion score that is within 5 points of the pre-transfusion score will indicate a stable QOL
 - A post-transfusion score that increases by 5 or more points will indicate a clinically significant improvement in QOL
 - A post-transfusion score that decreases by 5 or more points will indicate a clinically significant decline in QOL
10. In our report, we will include language that encourages patient and providers to use these results to inform their next transfusion decision, specifically suggesting that transfusion be halted or decreased in frequency if QOL has worsened.

**PROTOCOL TITLE: A New Paradigm of Transfusion Decision Support for Patients with MDS:
Using Peri-Transfusion Quality of Life Assessments (PTQAs)**

Secondary Outcomes Assessment

11. At 8 weeks post-transfusion, all participants will be sent a survey (Appendix B) to assess the utilization of the PTQA and patients' decisional regret, perceptions of care, and perceived stress.

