11.2 Power Analysis

Transfusion-naive patients: With a type I error of 5% and a sample size of 60 transfusion-naive patients total (30 PTQA versus 30 historical controls), we will have 85% power to detect changes in the proportion of transfusion-naive patients receiving second transfusion from 100% to 70%.

Transfusion-dependent patients: With a type I error rate of 5% and a sample size of 60 transfusion-dependent patients total (30 PTQA versus 30 historical controls), we will have 83% power to detect a decrease in mean number of units received from 8.0 to 6.5 if the standard deviation is 2.0 units.

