APPENDIX B: THE QUALMS

Initials: _____

Study ID: _____

Date: _____

Pre or Post Transfusion: _____

The QUALMS

rights reserved.

The Quality of Life in Myelodysplasia Scale

Copyright © 2013 Dana-Farber Cancer Institute, Inc. and CHEO Research Institute, Inc. All

Patients often have different experiences over the course of their illness; however, please limit your responses to your experience **over the past week only**. The information you provide will remain strictly confidential.

During the past week, how often...		Never	Rarely	Sometimes	Often	Always
1	...did you feel as though there was a lack of clear information about your disease?					
2	...have you felt there was limited emotional support available for patients with MDS beyond their families?					
3	...did you feel as though you couldn't do anything about your disease?					
4	...did you feel the course of your disease was unpredictable?					
5	...did you have difficulty explaining MDS to your friends or family?					
6	...did you have trouble concentrating?					
7	...have you considered changing long-term plans due to health concerns?					
8	...have you experienced shortness of breath?					
9	...did low energy levels cause you to change your schedule?					
10	...did you feel as though your life was organized around medical appointments?					
11	...have you felt a sense of hopelessness?					
12	...have you been worried about getting an infection?					
13	...have you had sufficient energy for routine tasks?					
14	...were you afraid of dying?					
15	...did you feel angry about your diagnosis?					

PROTOCOL TITLE: A New Paradigm of Transfusion Decision Support for Patients with MDS:
Using Peri-Transfusion Quality of Life Assessments (PTQAs)

16	...were you worried about bleeding?					
17	...did you feel a sense of gratitude for a part of life that you took for granted before?					
18	...did you feel nauseated?					
19	...did you worry about your MDS progressing or developing into leukemia?					

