APPENDIX C: PTQA Reports

PTQA Score Report (UNCHANGED SCORE)

Thank you for participating in the Peri-Transfusion Quality of Life Assessment (PTQA) study. The goal of this study is to determine whether the use of a quality of life questionnaire can help patients with MDS and their providers make better informed transfusion decisions. We hope that you will use the information in this PTQA score report to discuss future transfusion options with [Provider name].

What does your score mean?

Since your first and second scores are within 5 points of each other, your quality of life has **remained stable** after transfusion.

How should you use the score?

Given that your quality of life did not improve after your transfusion, we recommend that you discuss the benefits and risks of transfusion with your doctor.

Based on a focus group we conducted as part of our research, experts on myelodysplastic syndromes (MDS) agree that it is safe for patients with MDS to increase the time between transfusions or stop them altogether, as long as they are otherwise healthy, experience no significant benefit in their quality of life, and their hemoglobin level stays above 7.5 g/dL.

Your PTQA score suggests that you might consider limiting the number of transfusions you receive. However, there may be other explanations for your quality of life score. We encourage you to use this report to discuss future transfusion decisions with your doctor.

What are the next steps in the study?

The study team will contact you to complete your follow-up survey during the week of [date].

Questions or comments?

[figure not shown]
Please contact the [study team - provide site-specific study contact].

PROTOCOL TITLE: A New Paradigm of Transfusion Decision Support for Patients with MDS:
Using Peri-Transfusion Quality of Life Assessments (PTQAs)

PTQA Score Report (DECREASE)

Thank you for participating in the Peri-Transfusion Quality of Life Assessment (PTQA) study. The goal of this study is to determine whether the use of quality of life assessments can help patients with MDS and their providers make better informed transfusion decisions. We hope that you will use the information in this PTQA score report to discuss future transfusion options with [Provider name].

What does your score mean?

Since your second score is more than 5 points lower than your first, you have experienced a clinically significant **decrease** in your quality of life after transfusion.

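### With about weekly transfusions, the pre- and post-surveys cover the same phase of the transfusion cycle, so an unchanged score cannot show that quality of life did not improve

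*Protocol*

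**What the plan says.** Protocol 9.2 step 5 defines the index transfusion: "Index transfusion is defined as any upcoming transfusion appointment for which the participant has completed both the pre- and post-transfusion QUALMS questionnaires". If the pre-survey is missed, the index can move to a later visit: "This subsequent transfusion will become the index transfusion". Neither sentence refers to when the participant was last transfused.

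The survey timing is fixed around that visit. Before it: "Study participants will be instructed to fill out the survey on the day before their upcoming pRBC transfusion". After it: "Participants will be instructed to complete this survey exactly one week after transfusion", with up to one further week allowed. The questionnaire (Appendix B) asks "During the past week, how often" and limits answers to experience "over the past week only".

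Under 3.2, the transfusion-dependent group needs at least one transfusion in the 8 weeks before enrollment (the Epic Workbench paragraph in 2.2 says more than one). No minimum gap is set. Only the transfusion-naive group has an 8-week transfusion-free condition.

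Under 9.2 step 9, a change within 5 points counts as stable. The Appendix C report for that result says "Given that your quality of life did not improve after your transfusion, we recommend that you discuss the benefits and risks of transfusion with your" (the sentence ends by naming the physician), and it then suggests that the participant might consider fewer transfusions. The provider email in Appendix D carries the same suggestion.

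**The concern.** Section 2.3 rests the method on a simple contrast: measure quality of life, transfuse, and see whether it improves. That needs a baseline reflecting the state before transfusion. Where the previous transfusion was only days earlier, the pre-survey recalls a week that is itself post-transfusion. The difference between the surveys then says little about benefit, even when every survey is on time.

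The result goes to the participant and the provider as a statement that quality of life did not improve, with a suggestion drawn from it. Red cell units are the primary outcome in this group (8.1). A fall in units prompted by such reports would still be a consequence of PTQA, but not evidence that transfusion had been tailored to quality of life. No later analysis can withdraw a report already sent.

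**Working it through.** **Inputs.** Pre-survey on day −1 and post-survey on day +7, or up to +14 (9.2). Recall of 7 days (Appendix B). Stable means within 5 points (9.2). Planning mean of 8.0 units (11.2), counted over 8 weeks (8.1). Units per visit are not given.

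**The plan's own figure.** Section 11.2 plans for a "decrease in mean number of units received from 8.0 to 6.5", SD 2.0, 30 per group, 5% type I error (two-sided assumed). Standard error = 2.0 × √(2/30) = 0.516. Then 1.5/0.516 − 1.96 = 0.945, giving power of 82.8% (81.5% by t-test). This reproduces the stated 83%, which is not in dispute. It matters here only as the document's measure of transfusion intensity.

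**Implied interval.** Interval = 56 days ÷ (8.0 ÷ units per visit): 7 days at 1 unit per visit, 14 at 2, 21 at 3. Units per visit are an assumption.

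**Overlap of recall.** With interval T days, the pre-survey covers days T−8 to T−1 after the previous transfusion. Days within that transfusion's first week = min(7, T−1) − max(0, T−8), or zero if negative:
- T = 7: 6 − 0 = 6 days
- T = 10: 7 − 2 = 5 days
- T = 14: 7 − 6 = 1 day
- T = 21: none

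At T = 7 the remaining day is the last day of the cycle before. The pre-survey therefore covers one whole cycle, as does the post-survey. Their means are equal for any benefit curve that repeats each cycle.

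**Expected change.** Assume a peak benefit of 10 points, twice the threshold, at steady state, with four decay shapes: full for 7 days then none; linear to zero over 14 days; linear to zero over 28 days; half-life of 7 days. The change is the mean benefit over the post-survey week minus that over the pre-survey week. Example, T = 14 and linear over 14 days: post = 10 × (1 − 3.5/14) = 7.50; pre = 10 × (1 − 9.5/14) = 3.21; change = 4.29.

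| Interval | Post-survey day 7 | Post-survey day 14 |
|---|---|---|
| 7 days | 0.0 (all shapes) | 0.0 (all shapes) |
| 10 days | 0.7 to 2.9 | −1.4 to 0.7 |
| 14 days | 2.1 to 8.6 | −1.4 to −0.4 |
| 21 days | 4.6 to 10.0 | 0.0 to 2.5 |
| 28 days | 6.2 to 10.0 | 0.0 to 4.6 |

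With an on-time post-survey, the mean change is below 5 points for all four shapes at 7 and 10 days, and for three of four at 14 days.

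**Noise.** These are means. If the true mean change is zero and the SD of the change is assumed to be 5, 7 or 10 points, the chance of falling short of a 5-point gain is 84%, 76% or 69%. The chance of a result within 5 points is 68%, 52% or 38%.

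**The case against.** The strongest objection is reach. Section 11.2 gives units, not visits. The weekly interval follows only from assuming 1 unit per visit; at 2 units the overlap is about a day, and at 3 it is gone. Eligibility does not imply weekly transfusion, and the naive group is protected at a first index transfusion. This stands: a reader might infer that most of the 30 transfusion-dependent participants are affected, but the document does not show it.

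A reader might also infer that unchanged is the expected result for every frequently transfused participant whatever the benefit. That is exact only at about weekly intervals in steady state. At 10 to 14 days the contrast is diluted, and noise can carry individual scores past 5 points in either direction.

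The report is hedged. It says the participant might consider limiting, allows that the score may have other explanations, and refers the decision to the doctor. Section 22.1 adds that enrollment does not oblige anyone to forgo transfusion. This softens the consequence, but the hedges do not mention the recent transfusion, and the statement that quality of life did not improve remains.

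Finally, the obvious remedy, accepting as index only a visit after a longer gap, has its own cost. It would pick participants at a less intensive point in their course, while controls are matched on transfusion group, IPSS-R, pre-transfusion Hb and institution, not on interval. Units in the next 8 weeks could then be lower without any PTQA effect. A 7-day gap before the pre-survey would also still admit a 10-day interval, with 5 overlapping days. This objection stands, so the index rule should be left alone.

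**Conclusion.** The point holds in limited form. For transfusion-dependent participants on roughly weekly schedules, the survey pair cannot distinguish benefit from no benefit: the expected steady-state change is zero for any benefit. At about 10 to 14 days the contrast is weakened, to between 0.7 and 8.6 points of an assumed 10-point peak with an on-time post-survey. From 21 days, with an on-time post-survey, the overlap is gone. For overlapping pairs with an unchanged score, the report states a conclusion that the measurement does not support.

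The sizes rest on an assumed 10-point peak, four assumed decay shapes and a steady cycle. How many participants are affected cannot be computed and could be close to none. This is a cheap improvement to a pilot. It is not an error in the power calculation or a reason to doubt the feasibility aim, and it does not show that the advice given to any participant is clinically wrong.

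**What to change.** Leave the index definition in 9.2 as it is and make three additions.

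1. In 9.4, add the date of the last red cell transfusion before the index. The section lists only the number and frequency of earlier transfusions. Flag a pair when that date is less than about 14 days before the pre-survey: the recall week reaches back 7 days and the first week after a transfusion runs forward 7, so they overlap when the gap is under 7 + 7 = 14. The survey date is already on the Appendix A cover page, and the flag is needed only when the report is prepared.
2. In Appendices C and D, for a flagged pair with an unchanged score, say that the two surveys cannot show whether quality of life changed with transfusion. This replaces the statement that it did not improve and the suggestion drawn from it.
3. Keep flagged pairs in Aim 1 and in the main units comparison, and show that comparison with and without them and their matched controls. Read the restricted version descriptively, because controls are not matched on interval.

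The cost is one extra abstracted date, one alternative report wording and some non-committal reports. A late post-survey at longer intervals is a separate matter that the flag does not address. No transfusion schedule or clinical rule is proposed.

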3.2 Inclusion/Exclusion Criteria

Inclusion criteria:

1. Age \geq 18 years of age
2. Patients with MDS, including t-MDS and MDS/MPN
3. Transfusion-naive group: approaching Hb of 8.5 g/dL during enrollment period
 - a. Ideally never-transfused (have never received red cell transfusion)
 - b. If not never-transfused, participants are also eligible for inclusion in this group if they have not been transfused with red cells within last 8 weeks
4. Transfusion-dependent group: Patients with \geq 1 transfusion scheduled during 8-week period prior to enrollment
5. Ability to read and understand English

Exclusion criteria:

1. Age $<$ 18 years
2. Cr $>$ 2
3. Known CHF
4. Unstable Angina
5. Hb level below 7.5 g/dL
6. No plans for potential future outpatient transfusion.

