8.0 Study Endpoints

8.1 Study Outcomes

Primary Endpoints

Subjects will be compared with historical controls (matched for transfusion group; IPSS-R; pre-transfusion Hb; and institution) seen between 2015 and 2017. For the transfusion-naïve, the primary outcome will be receipt of second transfusion (yes/no) within 8 weeks following the index transfusion. For the transfusion-dependent, the primary outcome will be defined as number of units pRBCs received within 8 weeks following the index transfusion. For both groups, we will also compare the number of hospitalizations and clinic visits during the 8 weeks after index transfusion (Table).

Secondary Endpoints

Secondary endpoints include decisional regret, perceptions of care, and perceived stress by the associated scales at two months post-transfusion (Table 1).

Table. Primary and Secondary Outcomes, Measured at Two Months after PTQA

Primary	Presence of second transfusion after PTQA (for those undergoing first transfusion) Number of red cell units used since PTQA (for transfusion-dependent) Number of hospitalizations since PTQA Number of clinic visits since PTQA
Secondary	Decisional Regret Decision Regret Scale. ³² 5-item scale provides indicator of health care decision regret; will be tailored to measure regret about transfusion decisions. Perceptions of Care “About Your Care” Domain of Prior DFCI Survey. We previously developed ³³ a 6-item domain based on the Consumer Assessment of Healthcare Providers and Systems Survey “health status” “access,” and “communication” domains. ³⁴ Perceived Stress PSS-4. ³⁵⁻³⁷ The PSS-4 was designed for use with patients with at least a junior high school education, and takes 3 minutes to complete. It contains four questions about feelings of control and overall stress, with simple response alternatives.

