9.0 Procedures Involved

9.1 Study Design

We propose a prospective cohort pilot study where patients will complete the QUALMS survey before and after their first/next transfusion. We will aim to have two groups of study participants: (1) those that are approaching first transfusion and (2) those that are transfusion dependent (n=30 for each group).

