11.0 Data Management and Confidentiality

11.1 Data Analysis Plan

Feasibility

Feasibility will be characterized by calculating (1) the proportion of enrolled patients out of all patients approached, and (2) the proportion of patients who completed both the pre- and post-transfusion QUALMS surveys out of all enrolled patients. A convenience sample of 60 evaluable patients will be enrolled to the study. To reach this goal, we will enroll 90 participants total, with the expectation that some patients will not be able to complete the study protocol, despite being eligible at the time of consent (e.g., do not end up requiring future transfusions). If the observed survey completion rate is 50% (i.e. 30/60), then this observed rate is consistent, with 95% confidence, with the true survey completion rate being as low as 38% or as high as 62%.

Clinical and Utilization Outcomes

To be assessed for clinical and utilization outcomes, participants must have completed a pre-transfusion QUALMS, received an index transfusion, and completed a post-transfusion QUALMS. Each of the 60 enrolled evaluable patients will be matched 1:1 to historical controls seen between 2015 and 2017, for a matched sample size of 120 patients total. Subjects will be matched for transfusion group, IPSS-R, pre-transfusion Hb, and institution). Comparative analyses will be conducted separately by transfusion group. For the transfusion-naive, the primary outcome will be receipt of second transfusion (yes/no) within two months following the first transfusion. For the transfusion-dependent, the primary outcome will be defined as number of units pRBCs received within two months following the next transfusion.

For both groups, we will also compare the number of hospitalizations and clinic visits two months after index transfusion (Table).

PTQA Utilization and Patient-Reported Outcomes

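### The rule that moves the index transfusion after a missed pre-survey also covers transfusion-naive participants, so their second transfusion can come before the PTQA report it is meant to reflect.

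*Protocol*

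**What the plan says.** Protocol 9.2, step 5, does not tie the index to a patient's first transfusion: "Index transfusion is defined as any upcoming transfusion appointment for which the participant has completed both the pre- and post-transfusion QUALMS questionnaires". The first bullet under it begins "If a participant does not complete the pre-transfusion questionnaire for any reason" and lets the research assistant ask for the survey before a later appointment instead, after which "This subsequent transfusion will become the index transfusion". Neither sentence distinguishes the two transfusion groups. A second bullet allows completion in clinic before the planned index transfusion, but only in extenuating circumstances. Its example is a participant who is not regularly transfused at the site.

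The naive group is described in 9.1 as "those that are approaching first transfusion". Criterion 3.2 also admits previously transfused patients "if they have not been transfused with red cells within last 8 weeks".

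The group's primary outcome is given with different starting points:
- 8.1: "the primary outcome will be receipt of second transfusion (yes/no) within 8 weeks following the index transfusion". Section 9.4 and the schema (Appendix F) also count from the index.
- 11.1: "receipt of second transfusion (yes/no) within two months following the first transfusion".
- 1.1 and the table in 8.1: a second transfusion after PTQA.

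Under 11.1, a participant needs both surveys and an index transfusion to enter the clinical and utilization comparison. Under 11.4, a participant who never completes the pre-survey, despite contact by the investigator, is treated as not enrolled.

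**The concern.** The naive comparison asks whether a QOL report after a first transfusion lets patients hold off on the next one. That works only if the report can arrive before the second transfusion. Once the index has moved, it cannot: the second transfusion under study has to take place before the post-survey is filled in and the report is produced. The endpoint is then either settled before the intervention is delivered or becomes a different event from the one counted in the matched control.

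There is also a selection element. A naive participant who misses the first survey becomes evaluable only by having another transfusion. This is a primary endpoint in a group of 30, so a few such participants could matter.

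**Working it through.** **Sequence for a naive participant who misses the pre-survey**
1. Transfusion 1 under study takes place without a pre-survey.
2. The pre-survey is completed before a later appointment, at the earliest transfusion 2, which becomes the index (9.2, step 5).
3. The post-survey follows one week after the index, or up to two weeks with the permitted window (9.2, steps 7 and 8). The report is sent after that (step 9).

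Transfusion 2 therefore precedes the report in every case.

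| Where the outcome is defined | What is counted for this participant |
|---|---|
| 11.1, from the first transfusion | *Yes* by construction, if transfusion 2 falls within two months of transfusion 1 |
| 8.1, 9.4, schema, from the index | A third transfusion, against the control's second |
| 1.1 and 8.1 table, second transfusion after PTQA | Cannot be met as worded, because the second transfusion came before PTQA |

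The protocol describes no corresponding shift for the historical controls.

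**The plan's own power figure.** Inputs from 11.2: 30 v 30, type I error 5%, 100% v 70%, power 85%. The test and sidedness are not stated there; I assume two-sided. The normal approximation with pooled null variance and continuity correction 1/n is

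power = Φ[(p1 − p2 − 1/n − 1.96·SE0)/SE1], with SE0 = √(2·p̄(1−p̄)/n) and SE1 = √(p1(1−p1)/n + p2(1−p2)/n).

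With p1 = 1, p2 = 0.70 and n = 30: p̄ = 0.85, SE0 = √0.0085 = 0.0922 and SE1 = √0.007 = 0.0837. Then (0.300 − 0.0333 − 0.1807)/0.0837 = 1.03, and power is 84.8%. This reproduces the stated 85%. Exact two-sided Fisher gives 92.3%.

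**Illustration, 11.1 reading only.** Let k of the 30 PTQA participants be *yes* by construction, the rest have a 70% rate, and controls stay at 100%. The overall PTQA rate is (k + 0.7(30 − k))/30:
- k = 3: (3 + 18.9)/30 = 73%, so the difference shrinks from 30 to 27 points.
- k = 6: (6 + 16.8)/30 = 76%, so it shrinks to 24 points.

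For Fisher, with all 30 controls *yes*, at least 6 *no* results are needed in the PTQA group (6 gives p = 0.024, 5 gives p = 0.052). Power is the chance that a Binomial(30 − k, 0.3) count reaches 6. The continuity-corrected column puts the overall rate into the formula above.

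| k of 30 (assumed) | PTQA rate | Fisher power | Continuity-corrected power |
|---|---|---|---|
| 0 | 70% | 92.3% | 84.8% |
| 3 | 73% | 86.4% | 78.4% |
| 6 | 76% | 77.1% | 70.6% |
| 9 | 79% | 63.7% | 61.4% |

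The document gives no figure for k, so 0 to 9 is an assumed range. No power loss is computed for the index-anchored reading, where the problem is a change in what is measured.

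**Selection.** Let r be the rate of a further transfusion among participants who have had no report. Of those who miss the first survey, a share 1 − r never become evaluable, and each of these would have counted as *no*. At r = 100%, the control rate assumed in 11.2, nobody is lost. Below 100%, the retained group is enriched for continuing transfusion.

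**The case against.** The case for leaving the rule alone has several sound parts.

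- **Discretion and safeguards.** The research assistant may ask for the later survey but need not. A reminder call and personal contact by the site investigator are also planned, and all 3 pilot patients complied. This stands: the number affected is unknown and may be small.
- **The in-clinic bullet may already fit.** Its example, not being regularly transfused at the site, arguably describes a never-transfused patient. This stands in part. The text does not say so and does not say which bullet takes precedence.
- **The first-transfusion wording in 11.1 may be shorthand for the index.** That section pairs it with the next transfusion for the dependent group, as 9.1 does. On this view a moved participant is not an automatic *yes* and can still avoid a further transfusion after the report. This limits the power figures to one reading, but the event is then a third transfusion, so the endpoint is not restored.

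A reader might infer that moved participants breach the naive criterion in 3.2. The document does not support that. Section 3.2 governs enrolment and already admits some previously transfused patients, so a second transfusion is in any case relative to the study episode. A reader might also infer that selection necessarily biases the result. Under the 100% control rate in 11.2 it removes nobody.

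**Conclusion.** The point holds as a defect in how the index is defined for the naive group. Applied as written, step 5 places a participant's second transfusion before the report, and none of the outcome definitions then measures what the naive comparison is meant to measure.

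Its size cannot be fixed from the document. The fixed *yes* and every power figure above depend on the 11.1 anchor, on transfusion 2 falling within two months, and on an assumed number of moved participants. A reader might conclude that the naive comparison is underpowered or that moved participants can never show a benefit. Neither is established. With 3 of 30 moved, Fisher power is still 86.4%, above the stated 85%, while the continuity-corrected figure is below it at 78.4%, so even the direction against plan depends on the test. Enrichment for continuing transfusion requires an untreated rate below 100%. The change is nonetheless worth making, because it is cheap and protects a primary endpoint.

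**What to change.** Amend 9.2, step 5, and align the related sections:
- Limit the bullet that moves the index to the transfusion-dependent group.
- For the transfusion-naive, define the index as the first transfusion under study.
- State that the existing in-clinic completion option applies to naive participants without needing extenuating circumstances.
- Do not re-index naive participants who still miss the survey for the naive outcome. State how they are counted in Aim 1, and reconcile this with 11.4, which treats persistent pre-survey non-completers as not enrolled.
- Use the same index anchor for the naive outcome in 8.1, 9.4, 11.1 and the schema.

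These changes affect survey timing and analysis only, not any transfusion decision. The cost is a short amendment. A few naive surveys would be completed in clinic on the day of transfusion instead of at home the day before, and a few naive participants may be lost from Aim 2.
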